An ACT-Based Physician-Delivered Weight Loss Intervention

Study Protocol

[name], [name], & [name]

July 13, 2016

Study Protocol

The study was approved by the Research Ethics Board (REB-II) at McGill University (Montreal, Canada). Participants provided written informed consent prior to commencing the intervention.

Trial Design

The present study was a two-arm pilot randomized controlled trial conducted from May 7, 2016 to March 7, 2018. Participants were randomized to eight sessions of either an ACT-based intervention aimed at reducing emotional eating or standard care, which involved diet and exercise counselling. All outcomes were assessed at baseline and post-intervention. The present study aimed to recruit 128 participants (64 per condition), similar to the trial protocol outlined by [name] et al. (2014).

Participants

Participants were adults over the age of 18 with overweight or obesity who were seeking treatment for weight loss at a clinic in Toronto, Ontario. Only participants considered to be emotional eaters, as assessed by a score of 3.25 or higher on the Dutch Eating Behavior Questionnaire (DEBQ), were recruited for the study (van Strien, Herman, Anschutz, Engels, & de Weerth, 2012). In addition, participants who did not speak, write, and read in English fluently were excluded from the study, as well as those who were pregnant.

Study Procedures

Participants were recruited upon initial registration at the weight loss clinic. Those who expressed interest to participate were assigned a participant ID number and asked to complete a brief prescreen questionnaire to determine their eligibility based on the criteria described above. Eligible participants were randomly assigned to either the ACT intervention or control condition

based on the ID number they had initially received. Participants completed a battery of questionnaires both baseline and Session 8. Weight was measured every session.

Randomization and Blinding

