Participants were randomized in 1:1 sequence using a random number generator (randomizer.org). Two hundred participant ID numbers (1-200) were randomized prior to study commencement and assigned to patients who were prescreened. Due to a high number of ineligible participants, an additional 100 ID numbers (201-300) were randomized during the recruitment process. Participants retained the same ID number throughout, regardless of their eligibility, to simplify the process for administrative staff at the clinics. Participants were blind to their condition, but physicians and administrative staff were not blind to participant condition. Physicians were not blind to participant condition because they were responsible for delivering the ACT intervention or standard care. They were thus required to know the participant's condition in order to deliver the adequate treatment. Administrative staff was responsible for providing physicians with this information and organizing study paperwork and thus needed to be aware of participant condition as well.

Physician Training

Physicians were trained in the delivery of the weight loss interventions in a 1-hour Skype training session delivered by a clinical psychology PhD student. During this training session, each physician was taught how to administer the manualized ACT intervention and provided the opportunity to ask questions pertaining to the various skills that they would be required to teach their patients. Copies of the manual were provided to physicians to follow during sessions. Follow-up training sessions were conducted as necessary to ensure treatment fidelity and clarify questions that arose as physicians began delivering the interventions.

Intervention

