Participants in the standard care condition were provided with diet and exercise counselling and psychoeducation from their physicians over the course of 8 sessions, as was routinely done at the clinic. Physicians were responsible for facilitating this counselling at their discretion, and thus what “standard care” entailed differed based on the physician who was administering it. However, standard care did not involve any targeted intervention to reduce emotional eating. Thus, in addition to standard care, participants in the ACT condition were taught techniques to reduce their emotional eating. All sessions were approximately 5-10 minutes in length and weight was assessed at each visit. Three overarching skills were taught over the course of the ACT intervention: (1) values clarification and commitment, (2) metacognitive awareness, and (3) distress tolerance. ACT participants were first taught values clarification and commitment techniques, where they reflected on their reasons for losing weight and how this would improve their quality of life. Participants were taught the BOLD technique (Breathe, Observe sensations, Listen to values, Decide on actions that are in line with values) to use their values to make discussions pertaining to avoiding emotional eating (Ciarrochi, Bailey, & Harris, 2013). Next, participants were introduced to the concept of metacognitive awareness, or recognizing and identifying one’s thoughts, feelings, and emotions. Specifically, participants were trained in mindful eating, in order to increase awareness of hunger and satiety cues and avoid eating when not physically hungry (Kristeller & Wolever, 2011). Lastly, participants were taught to increase distress tolerance in the face of negative emotions that typically led to emotional overeating. Participants were taught acceptance techniques (dropping the rope, urge surfing) to use when experiencing triggering emotions or cravings (Bowen & Marlatt, 2009). An

intervention summary can be found in Table 1 and the intervention manual is available upon request.

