Throughout the sessions, physicians formed if-then plans with the patients to specify how to habitually use the ACT techniques to reduce emotional eating in their everyday lives. At the end of each session, participants were given a one-page homework sheet that asked them to monitor their behavior and their use of the ACT techniques during the week. Participants were instructed to bring the homework back with them for the next session so that it could be reviewed with their physician.

Measures

Demographics. At baseline, participants reported basic demographic information including gender, age, English fluency, ethnicity, marital status, educational attainment, employment status, household income, and whether or not they smoked.

Anthropomorphic measures. Weight was measured at each of the eight sessions (primary outcome). Participant body fat percentage was assessed and recorded by their physician at baseline and at completion of the eight sessions (secondary outcome).

Emotional, restrained, and external eating. Participants were pre-screened for emotional eating using the Dutch Eating Behavior Questionnaire (DEBQ; van Strien et al., 1986). The DEBQ is a 33-item questionnaire that assesses three dimensions of eating behaviors: emotional eating (primary outcome), restrained eating (secondary outcome), and external eating (secondary outcome). The emotional eating subscale assesses the reported desire to eat under specific negative emotional conditions such as stress, anxiety, and depression. The DEBQ has high internal consistency and factorial validity (van Strien et al., 1986). The DEBQ was administered again post-intervention.

Distress tolerance. The Distress Tolerance Scale (DTS; Simons & Gaher, 2005), a brief self-report questionnaire that assesses one's ability to tolerate distressing emotions, was completed at baseline and post-intervention (secondary outcome). The scale is made up of items that assess the dimensions of distress tolerance, absorption, appraisal, and regulation. The DTS has high reliability and high discriminant, convergent, and criterion validity (Leyro, Bernstein, Vujanovic, McLeish, & Zvolensky, 2011; Simons & Gaher, 2005).

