All analyses were conducted in SPSS version 24. 2 Two separate 2 (Condition: Standard Care, ACT Intervention) x 2 (Time: Baseline, Session 8) repeated measures MANOVAs were conducted for the anthropomorphic and questionnaire data outlined above, respectively, with follow-up *t*-tests conducted as necessary. Two separate MANOVAs were conducted to not lose data from incomplete cases (i.e., participants who had completed anthropomorphic but not questionnaire data). Independent samples *t*-tests were conducted for treatment satisfaction data collected at Session 8, whereas chi-square tests were conducted to compare recruitment rates, attrition rates, questionnaire completion, and intervention completion time between conditions. Missing data were not imputed because of the large drop out rates: Imputation with small sample sizes and high rates of missingness has been shown to be highly prone to Type I error (McNeish, 2016).

References

- Bowen, S., & Marlatt, A. (2009). Surfing the urge: brief mindfulness-based intervention for college student smokers. *Psychology of Addictive Behaviors, 23*(4), 666-671.
- [name], B., Ivanova, E., Xu, Z., Chamandy, M., Lowensteyn, I., Joseph, L., Luszczynska, A., & Grover, S. (2014). Increasing the effectiveness of the Diabetes Prevention Program through if-then plans: Study protocol for the randomized controlled trial of the McGill CHIP Healthy Weight Program. *BMC Public Health, 14*, 470.
- Kristeller, J., & Wolever, R. Q., (2011). Mindfulness-based eating awareness training for treating binge eating disorder: the conceptual foundation. *Eating Disorders, 19*(1), 49-61.
- Leyro, T. M., Bernstein, A., Vujanovic, A. A., McLeish, A. C., & Zvolensky, M. J. (2011). Distress Tolerance Scale: A confirmatory factor analysis among daily cigarette smokers. *Journal of Psychopathology and Behavioral Assessment, 33*(1), 47-57.
- Simons, J. S., & Gaher, R. M. (2005). The Distress Tolerance Scale: Development and validation of a self-report measure. *Motivation and Emotion, 29*(2), 83-102.

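### The MANOVAs pool the covariance of the two arms and no unequal-variance method is named, so if drop-out leaves unequal arms and the SDs of change also differ, the nominal error rate is not held

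*Combined protocol and SAP*

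**What the plan says.** All of this is in the combined protocol and SAP.

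- **Main test (Data Analysis).** Two separate 2 (Condition) x 2 (Time: Baseline, Session 8) analyses: "repeated measures MANOVAs were conducted for the anthropomorphic and questionnaire data outlined above, respectively". Follow-up t-tests are added where needed. Their type is not given.
- **Other tests (Data Analysis).** Independent-samples t-tests "were conducted for treatment satisfaction data collected at Session 8, whereas chi-square tests were conducted to compare recruitment rates, attrition rates" and some further process measures.
- **Missing data (Data Analysis).** "Missing data were not imputed because of the large drop out rates". No rate is given, overall or by arm.
- **Outcomes (Measures).** Weight is a primary outcome. "Participant body fat percentage was assessed and recorded by their physician at baseline and at completion of the eight sessions (secondary outcome"), which makes two anthropometric measures. The DEBQ gives "emotional eating (primary outcome), restrained eating (secondary outcome), and external eating (secondary outcome"). The distress tolerance, mindfulness and ACT-application scores are secondary.
- **Size and allocation (Trial Design; Randomization and Blinding).** "The present study aimed to recruit 128 participants (64 per condition"), with 1:1 allocation: "Participants were randomized in 1:1 sequence using a random number generator (randomizer.org").

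The plan does not mention equality of variances, Welch or another unequal-variance method, alpha, or the SD in either arm.

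**The concern.** With two measurement times, the Condition x Time test of a repeated measures MANOVA is Hotelling's T-squared on the change scores, with one covariance matrix estimated across both arms. With only two arms, Pillai, Wilks and the other MANOVA statistics all give the same F, so choosing among them offers no protection.

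Pooling is safe if the arms have similar spread, and close to safe if they have similar numbers. When neither holds, the test rejects too often if the smaller arm is the more variable one, and too seldom if the larger arm is. The plan reports large drop-out and analyses complete cases, so it cannot count on the planned balance surviving to Session 8. Each MANOVA also keeps its own set of complete cases. Both primary outcomes, weight and emotional eating, are tested this way.

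**Working it through.** **Inputs from the documents:** 64 per arm planned; 1:1 allocation; two anthropometric measures; drop-out described as large, with no figure.

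**Assumed, because the documents give no figure:** two-sided 5% level; normal change scores; no true difference; 32 v 32, 38 v 26 or 40 v 20 completers; SD ratio 1 or 1.5, the same for every outcome; seven questionnaire scores (three DEBQ, one distress tolerance, two mindfulness, one ACT application). There is no stated error rate or power to reproduce first.

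**Step 1: a single pooled t-test in closed form.** In large samples the actual error is

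2 x [1 − Φ(1.96 x √(P/V))],

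where P = {[(n₁−1)s₁² + (n₂−1)s₂²]/(n₁+n₂−2)} x (1/n₁ + 1/n₂) is the variance the test uses, and V = s₁²/n₁ + s₂²/n₂ is the true variance of the difference.

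- *Equal SDs, 40 v 20:* P = V = 0.075, so P/V = 1 and the error is 5%.
- *Equal arms, 32 v 32, SD ratio 1.5:* P = V = 0.1016, so the error is again 5%.
- *38 v 26, smaller arm more variable:* P = [(37 + 25 x 2.25)/62] x 0.06478 = 0.0974; V = 1/38 + 2.25/26 = 0.1129; P/V = 0.863; error 6.9%.
- *38 v 26, larger arm more variable:* P = [(37 x 2.25 + 25)/62] x 0.06478 = 0.1131; V = 2.25/38 + 1/26 = 0.0977; P/V = 1.158; error 3.5%.
- *40 v 20, smaller arm more variable:* P = [(39 + 19 x 2.25)/58] x 0.075 = 0.1057; V = 1/40 + 2.25/20 = 0.1375; P/V = 0.769; error 8.6%.
- *40 v 20, larger arm more variable:* P = [(39 x 2.25 + 19)/58] x 0.075 = 0.1380; V = 2.25/40 + 1/20 = 0.10625; P/V = 1.299; error 2.5%.

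Both conditions, unequal numbers and unequal SDs, are needed.

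**Step 2: the MANOVAs by simulation.** Hotelling's T-squared was computed on change scores with pooled covariance and referred to F with p and n₁+n₂−p−1 degrees of freedom, at an SD ratio of 1.5. Each cell shows the error when the smaller arm is more variable, then when the larger arm is.

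| Test | 38 v 26 | 40 v 20 |
|---|---|---|
| 7-score MANOVA | about 10% / 3% | about 14% / 1.6% |
| 2-measure MANOVA | about 7.5% / 3% | about 10% / 2% |
| Pooled t-test | about 7% / 3.5% | about 8.6% / 2.6% |

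At 32 v 32 with the same SD ratio, all three tests stay between about 5% and 6%.

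**Step 3: unequal-variance versions.** Welch's t-test and an unequal-covariance Hotelling test (modified Nel-van der Merwe degrees of freedom) stayed at about 4.5% to 5.7% in these settings.

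**Step 4: how much differential loss this needs.** From 64 per arm, 38 v 26 completers means 26/64 = 41% v 38/64 = 59% lost. On a two-proportion test, z = 0.1875/√(0.5 x 0.5 x 2/64) = 2.12, p about 0.03. For 40 v 20 the loss is 24/64 = 37.5% v 44/64 = 69%, with z = 0.3125/√(0.469 x 0.531 x 2/64) = 3.54, p about 0.0004.

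**The case against.** The case against is substantial, and much of it stands.

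- **Neither condition is shown.** Allocation is 1:1, and no drop-out figure by arm is given. Comparing attrition between arms is routine in a pilot and is not evidence that it differs. The imbalances used above would be unlikely by chance, and the plan's own attrition test would tend to flag them. This stands, and it makes the point conditional.
- **Equal spread may be plausible.** A reader might infer unequal spread from the Intervention section, where what standard care "entailed differed based on the physician who was administering it". The documents do not support that: the ACT arm received its techniques in addition to standard care, so variation between physicians is present in both arms. If the intervention did nothing, randomisation would give equal distributions, and unequal spread would have to come from who dropped out.
- **The t-tests may not pool.** A reader might infer that they do. The plan does not say, SPSS prints the unequal-variance row beside the pooled one, and some follow-ups may be paired within an arm, where nothing is pooled between arms. For the t-tests the gap is an unstated choice, not a demonstrated error.
- **Selection is the larger threat.** With loss as unequal as 37.5% v 69%, bias from who remained matters more than the variance estimate, and Welch does not cure it. This stands too.

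What survives is that the named main test pools by construction, the plan describes large unimputed drop-out, and nothing in it guards against the combination.

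**Conclusion.** The concern holds in conditional form, as an inexpensive improvement to the plan. The MANOVAs rely on equal covariance in the two arms or nearly equal numbers of completers, and the plan secures neither. At an assumed SD ratio of 1.5, a moderate imbalance (38 v 26) moves a nominal 5% to somewhere between about 3% and 10%, depending on the test and on which arm is more variable. A strong imbalance (40 v 20) moves it to between about 1.6% and 14%.

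Two stronger readings should be resisted. Unequal arms alone do not distort the error rate. Nor is 14% an estimate for this trial or for all its tests: it belongs to one assumed case, seven scores at 40 v 20 with the smaller arm 1.5 times as variable on every score. Level, completer numbers, SD ratio and number of scores are all assumptions.

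**What to change.** State in Data Analysis that between-arm tests do not assume equal variances:

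- For each outcome, compare the arms by Welch's t-test on change from baseline to Session 8 (the SPSS row for equal variances not assumed), or by a baseline-adjusted model with robust (HC3) standard errors.
- Use the Welch row for treatment satisfaction as well, without a preliminary test of variances.
- Say whether each follow-up t-test is between arms or within an arm.
- If an omnibus test is kept, use an unequal-covariance Hotelling test on the change scores. This may need software other than SPSS.
- Report the number of completers and the SD of change by arm, so that a reader can see whether the issue arose.

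**Cost:** a few sentences and no new data. If variances are in fact equal, the power loss is under 1 point: 71.1% v 70.3% at 40 v 20 for an assumed effect of 0.7 SD. Bias from differential drop-out remains and has to be addressed separately.

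### Splitting the analysis into two MANOVAs protects cases between blocks but not within them: a missing secondary measure can remove a primary outcome that was measured

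*Combined protocol and SAP*

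**What the plan says.** Data Analysis specifies two 2 x 2 "repeated measures MANOVAs were conducted for the anthropomorphic and questionnaire data outlined above, respectively, with follow-up" t-tests where needed. The within-subject factor has two levels, "Time: Baseline, Session 8". The reason given for two models is "Two separate MANOVAs were conducted to not lose data from incomplete cases", and the example given is "participants who had completed anthropomorphic but not questionnaire data". The same section states that missing values were not imputed.

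The Measures section shows what falls in each block:

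- **Anthropomorphic block.** Weight is primary: "Weight was measured at each of the eight sessions (primary outcome"). Body fat is secondary: "Participant body fat percentage was assessed and recorded by their physician at baseline and at completion of the eight sessions (secondary outcome").
- **Questionnaire block.** The DEBQ supplies "emotional eating (primary outcome), restrained eating (secondary outcome), and external eating (secondary outcome"). The Distress Tolerance Scale (DTS), the Philadelphia Mindfulness Scale (PHLMS) and the ACT application questionnaire are further secondary outcomes, each completed at baseline and post-intervention.

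No separate model is specified for weight or for emotional eating.

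**The concern.** The plan recognises that a joint model loses incomplete cases and deals with this at one level only, between the two blocks. The same mechanism works inside each block, where each primary outcome shares a model with secondary measures.

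The people affected reached Session 8 and have the primary value at both times. Dropping them costs precision in a trial whose Data Analysis section already reports heavy dropout. It also restricts the primary comparison to participants whose secondary measures are complete, a narrower group than those with the primary outcome measured.

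**Working it through.** **The plan's own figure.** The only sample-size figure is the target of 128 (64 per condition) in Trial Design. No effect size, SD, alpha, power or dropout rate accompanies it, so it cannot be reproduced from the document. The point does not depend on it. For reference, an assumed standardised difference of 0.5 with two-sided alpha 0.05 and 80% power needs 63.77, so 64, per arm by the t-based calculation. This is compatible with the target but does not show how it was chosen.

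**Step 1: what the model needs.** Each MANOVA uses the full set of dependent variables at both times. Without imputation, a case missing any one of them drops out. As a demonstration, a simple two-group MANOVA was fitted (not in SPSS) to 128 simulated cases with complete weights and 13 body-fat values removed. It kept 128 − 13 = 115 cases, so 13 measured weights were lost.

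**Step 2: how many extra items each primary outcome depends on.**

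- Weight: body fat at two times, k = 2.
- Emotional eating: DTS, PHLMS and ACT application at two times, k = 3 × 2 = 6. Restrained and external eating are on the same DEBQ form and are not counted.

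**Step 3: the added loss.** The documents give no missingness per reading or form, so q below is an assumption. If each extra item is missing independently with probability q, the share of complete primary pairs lost is 1 − (1 − q)^k.

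| q | Weight, k = 2 | Emotional eating, k = 6 | Emotional eating, forms missed at Session 8 only, k = 3 |
|---|---|---|---|
| 2% | 1 − 0.98² = 4.0% | 1 − 0.98⁶ = 11.4% | 1 − 0.98³ = 5.9% |
| 5% | 1 − 0.95² = 9.8% | 1 − 0.95⁶ = 26.5% | 1 − 0.95³ = 14.3% |
| 10% | 1 − 0.90² = 19.0% | 1 − 0.90⁶ = 46.9% | 1 − 0.90³ = 27.1% |

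**Step 4: the lower end.** If the extra items are missing only when the primary outcome is missing too (whole battery or whole visit), the added loss is 0%. Positive correlation that falls short of this gives values between zero and the table.

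**Step 5: in participants.** With 64 per arm and no dropout, separate models keep 64 per arm. At q = 10% the joint models keep 64 × 0.810 = 51.8 per arm for weight and 64 × 0.531 = 34.0 for emotional eating. For a simple t-test with the assumed difference of 0.5, power falls from 80% to 71% and 53% respectively. These figures illustrate scale and are not predictions for this trial.

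**The case against.** **Missingness may come in whole blocks.** Study Procedures describes one set of questionnaires at baseline and Session 8, and the only partial missingness Data Analysis describes is of the entire questionnaire block. Body fat was recorded at visits where weight was also taken, and nothing documents it missing when weight is present. If so, little or nothing is lost beyond dropout. This stands, and it is why the range starts at zero. It is not conclusive. Measures says the DEBQ was used for pre-screening and given again afterwards. If the pre-screen score serves as baseline, which the text suggests but does not state, an entry score could exist without the other baseline forms.

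**The follow-up t-tests could use every available value.** They could, but they are run only as needed and no case set is given. They do not guarantee recovery of the dropped values.

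**Deletion is not named.** True. It follows from this model combined with the decision not to impute.

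**The split does what it set out to do.** It does keep participants with one block and not the other. A reader might infer that the plan brings about the very loss it set out to prevent. Its stated example is narrower than that, and the fair criticism is that the protection is incomplete.

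**Differential loss by arm.** A reader might also infer that form completion differs because the ACT arm has more paperwork. The documents do not support this for the analysed measures, which are described without any difference by arm. The extra ACT paper is homework, which enters neither MANOVA. Data Analysis also already compares questionnaire completion between conditions. That comparison would show a difference by arm, though it restores no lost case.

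**Conclusion.** The point holds as a structural weakness of uncertain size. It follows from the stated model, the outcome list and the absence of imputation that a measured weight or emotional eating score can be excluded because a secondary measure is missing, and nothing in the plan guarantees its recovery.

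The added loss is never a gain and may be nil. Under independent loss of 2% to 10% per reading or form per time, it is 4% to 19% of weight pairs and 11% to 47% of emotional eating pairs. Both the rates and the independence are assumptions, and the upper figures should not be read as estimates for this trial. In a pilot where dropout is the dominant loss, this is a change worth making mainly because it is cheap.

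**What to change.** In Data Analysis, state that weight and DEBQ emotional eating are each analysed in their own model, in all eligible randomized participants with that outcome measured at baseline and Session 8, whether or not body fat or any other questionnaire is present. The word eligible is needed because, under Randomization and Blinding, ID numbers were randomized before eligibility was known and were kept by ineligible people. Keep the MANOVAs, if wanted, for the secondary outcomes. Report the number analysed for each outcome in each arm.

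The cost is a short addition to the text and two simple models in SPSS, using data already collected. The number analysed will differ between outcomes, and participants who dropped out before Session 8 are not recovered.

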Mindfulness. At both time points (i.e. baseline, post-intervention) participants completed the Philadelphia Mindfulness Scale (PHLMS; Cardaciotto, Herbert, Forman, Moitra, & Farrow, 2008), a 20-item self-report questionnaire that assesses two components of mindfulness: present-moment awareness and acceptance (secondary outcome). The scale has been shown to have good internal consistency and construct validity (Cardaciotto, Herbert, Forman, Moitra, & Farrow, 2008).

ACT application. At baseline and post-intervention participants filled out a self-report questionnaire designed to assess the extent of the participant's use of ACT strategies to reduce emotional eating (secondary outcome). This questionnaire was developed for the present study to evaluate participants' real world application of the intervention. Participants were asked to indicate their level of agreement on a 5-point scale (1 = strongly agree and 5 = strongly disagree) to prompts such as "My values motivate me to lose weight" and "I am able to accept negative emotions and don't have to eat when I'm feeling bad".

Treatment satisfaction. After the eighth session, participants completed a brief, self-developed questionnaire to assess their overall satisfaction with the intervention. Participants were asked to indicate their level of agreement on a 5-point scale (1 = strongly agree and 5 = strongly disagree). Physicians were also asked to complete a similar questionnaire at various

points throughout the intervention to obtain their input on its feasibility and efficacy of the intervention. Open-ended feedback was also collected from physicians, asking for their suggestions on ways to improve the intervention, and to provide insight on patient dropout/non-responsiveness.

Data Analysis

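### In a trial labelled a pilot, recruitment, attrition and questionnaire completion are planned only as between-arm chi-square tests, which say nothing about the absolute rates; report proportions and arm differences with 95% intervals

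*Combined protocol and SAP*

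**What the plan says.** The Trial Design section states: "The present study was a two-arm pilot randomized controlled trial". It adds a recruitment target: "The present study aimed to recruit 128 participants (64 per condition"). For the process measures, the Data Analysis section gives one method: "chi-square tests were conducted to compare recruitment rates, attrition rates, questionnaire completion, and intervention completion time between conditions". It plans no overall or per-arm estimate with an interval, and sets no target rate or progression criterion.

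The same paragraph reports heavy dropout: "Missing data were not imputed because of the large drop out rates". The Randomization and Blinding section says that ineligibility was common enough for 100 further ID numbers to be randomized on top of the first 200.

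Other feasibility material is collected. Independent-samples t-tests "were conducted for treatment satisfaction data collected at Session 8", which is again a comparison between arms. Physicians completed a questionnaire to "obtain their input on its feasibility and efficacy of the intervention" and gave open comments on dropout, but no analysis of either is described.

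This point covers the first three measures in the chi-square sentence. The fourth, completion time, reads as a duration. A chi-square would suit it only if it were categorised, and no categories are given.

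**The concern.** A pilot is usually expected to show what share of patients can be recruited, kept to the last session and assessed. Those are questions about absolute levels. A chi-square between arms asks only whether two rates differ. If both arms keep nearly everyone, or both lose nearly everyone, its expected answer is the same.

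Two misreadings are possible when the p-value is the planned result. A non-significant attrition test could be taken to mean that retention was adequate, which it cannot show. It could also be taken to mean that the arms had equal retention, for which it is weak evidence at this sample size. Both matter here because the plan itself describes dropout as large.

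Recruitment has a further problem. Condition was tied to the ID number, and the ID was issued before eligibility was known. Participants are described as blind to condition, while physicians and administrative staff were not. A difference between arms in the share enrolled therefore points to chance or selection and not to the acceptability of ACT. The informative recruitment figures, eligible out of prescreened and enrolled out of eligible, are not planned.

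**Working it through.** **Inputs.** From the documents: 64 per arm (Trial Design), 1:1 allocation ("Participants were randomized in 1:1 sequence using a random number generator"), and the chi-square test (Data Analysis). Assumed: a two-sided 5% level and no continuity correction. The documents give no attrition figure, so equal true rates from 10% to 90% were tried, and all counts below are illustrative.

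**The plan's own figure.** The 64 per arm comes without effect size, SD, level or power, so it cannot be reproduced from the documents. As an assumption only, a standardised difference of 0.5 with 80% power gives 2 × (1.960 + 0.842)² / 0.5² = 62.8, that is 63 per arm (64 with the t distribution). Nothing below depends on this.

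**Step 1: equal attrition in both arms.** The probability of a non-significant result is the sum of Bin(x₁; 64, p) × Bin(x₂; 64, p) over all pairs of counts with chi-square ≤ 3.841.

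| True attrition, both arms | P(non-significant) |
|---|---|
| 10% | 0.949 |
| 20% | 0.952 |
| 50% | 0.955 |
| 60% | 0.946 |
| 70% | 0.949 |
| 90% | 0.949 |

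With Yates correction the values are 0.97 to 0.98. Observed counts of 45/64 v 45/64 lost and 6/64 v 6/64 lost both give p = 1.0.

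**Step 2: unequal attrition.** Approximate power = Φ[(|p₁ − p₂| − 1.96 s₀) / s₁], with s₀ = √(2p̄(1 − p̄)/64) and s₁ = √(p₁(1 − p₁)/64 + p₂(1 − p₂)/64).

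- 50% v 65%: s₀ = 0.0874, s₁ = 0.0864; (0.15 − 0.1713)/0.0864 = −0.246, power 0.40. Exact enumeration gives 0.41.
- 50% v 60%: s₀ = 0.0879, s₁ = 0.0875; (0.10 − 0.1724)/0.0875 = −0.827, power 0.20. Exact enumeration gives 0.20.
- In the other direction, 10% v 30% is significant with probability 0.82, although both arms then keep most patients.

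These figures apply to attrition and questionnaire completion. They do not apply to recruitment, whose denominator is the prescreened patients (up to 300 IDs).

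**Step 3: what an interval would show.** Wilson limits are [p + z²/2n ± z√(p(1 − p)/n + z²/4n²)] / (1 + z²/n), with z = 1.96 and n = 64, so z²/n = 0.0600.

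- 26/64 retained: centre (0.4063 + 0.0300)/1.0600 = 0.412, half-width 0.117. This is 41%, 95% CI 29% to 53%.
- 45/64 retained: centre (0.7031 + 0.0300)/1.0600 = 0.692, half-width 0.109. This is 70%, 95% CI 58% to 80%.

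The two intervals do not overlap, so at the planned size they separate poor from good retention.

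**Step 4: what an interval for the difference would show.** For 45/64 v 45/64, combining the Wilson limits by Newcombe's method gives 0 ± √((0.7031 − 0.5823)² + (0.8010 − 0.7031)²) = ± 0.155. Identical observed rates, with p = 1.0, are still compatible with a true difference of about 16 percentage points either way.

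**The case against.** The strongest reply is that the plan never sets feasibility as an objective and never calls the chi-square a feasibility criterion. The named primary outcomes are weight and DEBQ emotional eating. This is correct. The feasibility aim is an inference from the pilot label, the process measures chosen and the physician questionnaire.

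The test also has a proper use. The MANOVAs are run without imputation, so attrition or questionnaire completion that differs by arm could bias them, and comparing arms is a normal check. With unblinded staff and condition attached to the ID, comparing recruitment by arm can likewise reveal selection. Both uses stand. An estimate with an interval serves them better than a p-value alone.

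The raw rates come with the chi-square tables, and satisfaction scores and physician feedback are collected as well. This too is correct, so the gap is in planned estimates and their precision, not in data. Those other sources do not fill it: satisfaction is compared only between arms and is collected after the eighth session, and the physician material has no stated analysis.

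Finally, non-significance 95% of the time under equal rates is simply what a 5% test does. That is so, and it is why the test cannot speak to the level of a rate.

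**Conclusion.** The point holds as a cheap improvement to the analysis. The only stated analysis of recruitment, attrition and questionnaire completion is silent on absolute rates, being non-significant about 95% of the time from 10% to 90% common attrition. It also gives weak evidence of similar attrition, with power of about 0.41 for 50% v 65% and 0.20 for 50% v 60%. This rests on 64 per arm, an assumed two-sided 5% level and illustrative rates.

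A reader might infer more than this, and the documents do not support it:

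- That feasibility is judged solely by the chi-square, or that the feasibility question goes unanswered. No such rule is written, and other feasibility data are collected.
- That the programme lost most of its patients. Dropout is called large, but no figure is given.
- That the investigators would present a non-significant test as support for ACT. Nothing in the text says so.
- That comparing the arms is an error. It is a legitimate check, but it is incomplete as the only analysis.

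**What to change.** In the Data Analysis section, add or substitute the following:

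1. Report eligible/prescreened and enrolled/eligible, overall, with 95% Wilson intervals.
2. Report the proportions reaching Session 8 and completing the Session 8 questionnaires, overall and per arm, with 95% Wilson intervals.
3. Give the arm differences in attrition and in questionnaire completion as estimates with 95% confidence intervals, in place of or alongside the chi-square p-values.
4. Interpret recruitment by arm only as a check on allocation and selection.
5. State that a non-significant test will not be read as evidence of adequate or equal retention.
6. Label any retention threshold set now as post hoc. The plan is written in the past tense and already refers to large dropout, so such a threshold cannot be presented as prespecified. The intervals need no threshold and can be reported in any case.

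The cost is a few lines of text and some intervals from counts that the chi-square tests and prescreening should already have produced. The downside is slightly longer reporting. Wide intervals or low retention may also look less favourable than a neutral test result.
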